**5. Patient Eligibility and Recruitment**

We will recruit an ethnically diverse sample of eligible patients ( $N = 1,500$ , 750 men, 750 women, evenly distributed across White, African-American, Hispanic/Latino) to complete the intervention.

Eligibility criteria: patients must be between the ages of 45 and 73, able to read English or Spanish at least at eighth-grade level, have an email account or the ability to receive texts, and be out-of-guidelines for CRC screening within recommended guidelines (i.e., <10 years for colonoscopy, <3 years for Cologuard, <1 year for FIT). The primary outcome in the current study is CRC screening compliance. Compliance will be assessed by electronic medical record review (MRR) at 6, 12, and 18 months after enrolling in the study. Patients will be considered compliant if they a) complete a home stool test with a negative result only, b) complete a home stool test with a positive result AND undergo a completion screening colonoscopy, c) complete Cologuard only, or d) complete a colonoscopy only. We will also examine potential mediators of intervention effectiveness, such as exposure to the intervention, psychological processing of content (e.g., comprehension, perceived message quality), and online records of communication with a healthcare provider about screening.

Recruitment locations: Online at University of Florida Health, online through social media and online at community events (e.g., UFHealth Cancer Center (UFHCC) Office of Community Outreach and Engagement (COE), Community Clinical Navigation (CCN) and Mobile Outreach Clinic (MOC)).

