After completion of the interaction patients will also complete a brief questionnaire (Post-intervention screener) to assess interest in screening, their screening status, and CRC risk. For patients who are unsure of their screening status or risk-level, project staff will conduct medical record review and/or consult with the PCP. Patients at low/average risk will be asked whether they would like to request a FIT test. Patients at high-risk will be asked whether they would like to speak with their primary care physician about colonoscopy. For all patients regardless of risk-level who click “Yes,” the system will send a request to their primary care physician to consult with the patient. If a FIT order is approved, we will then send the appropriate FIT kit to the participant at the requested address. Participants will be reminded to complete and return their kits to their clinic or lab at 2 weeks (English and Spanish - FIT Kit Reminder A Script; e-mail), 4 weeks (English and Spanish - FIT Kit Reminder B Script; text message), and 6 weeks (English and Spanish - FIT Kit Reminder C Script; phone message) after being mailed the kit.

For patients accessing the intervention through UF Qualtrics, screening status and risk will again be assessed with a similar procedure. For the patient FIT request message, an additional item will be included on the questionnaire asking them if they would like to request a FIT test. For patients choosing “Yes,” physical address as well as email will be collected and stored in UF Qualtrics.

After questionnaire completion patients will be directed to a compensation survey where name, physical address, and email are collected for the purpose of distributing study compensation.

One month after the initial invitation and reminders (Phase 2), participants who have not completed Phase 1 of the intervention or did not request screening after completing Phase 1 of the intervention, will be re-contacted through MyUFHealth or email and re-invited to the study. Participants will be remunerated \$10.00 for completing the intervention at Phase 2.

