In Phase 3, participants who respond to the intervention will receive an invitation in MyUFHealth or email 12 months after the date of their initial recruitment inviting them to click on a link to receive a booster message encouraging regular, repeated screening and offering them the opportunity to request their annual FIT kit from their provider. Participants will then complete 5-10 short questions relevant to their

experience with FIT (e.g., “How easy was it for you to follow the instructions that came with your FIT test?”) and any pertinent changes to their health history (e.g., “Has anyone in your family been diagnosed with colorectal cancer in the past year?”). Participants will be remunerated \$5.00 for completing the booster questionnaire.

In addition to the post intervention test, we will monitor Epic for participants' screening compliance (to determine whether they have engaged in behavioral change), whether they make appointments with their doctors (to establish whether they engage in informed decision-making with their healthcare provider) and whether they request repeat testing the following year (to track long-term behavioral change). We will also track whether people were diagnosed with CRC to see whether the intervention has significant impacts on detection of CRC rates among participants.

To ensure that our technology systems are functioning as expected and that patients have received their mailed FIT kits, we will conduct quality control calls with patients who do not finish the intervention, who do not respond to recruitment messages, or who do not have screening results entered into their MR. A research coordinator or community health worker (CHW) will call patients and ask if they encountered any technical difficulties in using the intervention, or if they received their FIT kit and encountered any difficulty using it. If the patient encountered technical problems, we will gather relevant details (such as web browser used) and pass this information along to our technology team. This will allow them to troubleshoot problems and increase completion rates. If the patient encountered problems with screening, we will again gather relevant details and provide the needed guidance/support.

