## **6. Study Design**

We will evaluate the VHT intervention using a fractional factorial experimental design embedded within a sequential, multiple assignment, randomized trial (SMART). The fractional-factorial design allows estimation of the optimal tailored message assuming only lower-order interactions and requires far fewer samples. For example, a full factorial design of 10 factors at two levels would involve runs of size 4,096 whereas a fractional factorial design that does not confound any pairwise interactions would involve runs of size 79. In short, the fractional factorial experimental design allows us to go beyond simply testing the efficacy of tailored vs. non-tailored messages by honing in on the specific elements of a message that are most salient to the patient.

We will also collect longitudinal data on outcomes associated with exposure to the intervention (Phase 3). Participants in the treatment arms who have completed their initial screening within the first 12 months of the study will receive an email invitation one year after the intervention. This message will invite them to view a booster of the intervention consisting of another message encouraging repeated screening. Compliance will be assessed via self-reporting and MRR for all patients as well as through tracking in MyUFHealth.

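### Phase 2 entry turns on a screening request and exempts no one already screened, and requesters who never screen have no stated second stage

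*Combined protocol and SAP*

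**What the plan says.** Section 6 describes a SMART with an embedded fractional factorial design, and its Sample Size Analysis applies the factorial message combinations at each stage of randomization. Who enters the second stage is therefore part of the design.

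- **Phase 2 entry (Section 5).** The time point is "One month after the initial invitation and reminders (Phase 2"). Those re-invited are "participants who have not completed Phase 1 of the intervention or did not request screening after completing Phase 1 of the intervention".
- **What a request does (Section 5).** After a Yes, "the system will send a request to their primary care physician to consult with the patient". A kit is mailed only if an order is then approved. "Participants will be reminded to complete and return their kits to their clinic or lab at 2 weeks", and again at 4 and 6 weeks, counted from mailing.
- **What is known about screening status (Section 5).** Patients must "be out-of-guidelines for CRC screening within recommended guidelines" at entry. The post-intervention screener is given "to assess interest in screening, their screening status, and CRC risk", with record review or a physician consultation for those unsure. Epic is monitored for screening.
- **Primary outcome (Section 5).** Completed screening, by record review at 6, 12 and 18 months.
- **Phase 3 entry.** Section 5: "participants who respond to the intervention will receive an invitation in MyUFHealth or email 12 months after the date of their initial recruitment". Section 6: "Participants in the treatment arms who have completed their initial screening within the first 12 months of the study".

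**The concern.** For Phase 1 completers, the variable that decides a second message is a request, and the outcome is a completed screen. The two can disagree in both directions.

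First, a patient may be screened, or be found up to date, without having requested anything. As written, that patient goes to Phase 2. A second message cannot alter initial screening that is already done, so the patient adds noise and no information to the second-stage comparison.

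Second, a patient may request and never screen. That patient is not in Phase 2 and, by the Section 6 wording, not in Phase 3 either. Second-stage results could then be read as applying to everyone who failed to screen, when they cover only non-requesters and Phase 1 non-completers.

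Behind both lies a wording problem. Phase 2 speaks of requesting, Section 5 on Phase 3 speaks of responding, and Section 6 speaks of completing. None of these is defined as the response status on which the sequential design branches.

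**Working it through.** **Plan's own figure.** The plan gives no request, kit-return or already-screened rate, so it has no figure on this point to reproduce. Its one checkable sample-size step holds: 1,000 / (1 - 0.33) = 1,493, in line with the stated 1,500. That step carries no information about Phase 2.

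**Tracing each patient type through the entry rules**

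- *Completed Phase 1, requested, screened within 12 months:* not Phase 2; Phase 3 under either wording.
- *Completed Phase 1, requested, never screened:* not Phase 2; not Phase 3 under Section 6; unclear under Section 5, because responding is undefined.
- *Completed Phase 1, no request, not screened:* Phase 2.
- *Completed Phase 1, no request, already screened or confirmed up to date:* Phase 2, because no exemption is written.
- *Did not complete Phase 1:* Phase 2, whatever the screening status.

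The second and fourth types are the problem.

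**Timing.** Taking a month as about 30 days from the invitation, the 6-week reminder for a kit mailed on the invitation day would fall 42 - 30 = 12 days after the Phase 2 point. Kits are mailed later than that, after physician approval. A completed test is therefore not yet observable for many requesters at one month, and the first scheduled record review is at 6 months.

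**Attenuation.** Let f be the share of non-requesters whose initial screening cannot change. If second-stage randomization spreads them evenly over the message combinations and their effect is zero, then

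observed difference = (1 - f) x difference among those who can change.

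- f = 0.02: factor 0.98, a 2% loss.
- f = 0.10: factor 0.90, a 10% loss.

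For scale only, using the plan's 0.075 margin as the difference: 0.075 x 0.98 = 0.0735, and 0.075 x 0.90 = 0.0675. These factors apply to non-requesters. Phase 1 non-completers are also in the pool, and their share is not given.

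**Counts per 1,000 Phase 1 completers, all rates assumed.** Let r be the share requesting (0.3 to 0.7) and k the share of requesters returning a kit (0.4 to 0.8).

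- Needlessly re-invited = 1,000 x (1 - r) x f. Low: 1,000 x 0.3 x 0.02 = 6. High: 1,000 x 0.7 x 0.10 = 70.
- Requesters with no returned kit = 1,000 x r x (1 - k). Low: 1,000 x 0.3 x 0.2 = 60. High: 1,000 x 0.7 x 0.6 = 420.

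The second range measures only the assumed rates. It also overstates the group without a screen to the extent that some non-returners are screened another way.

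**The case against.** Much of the case on the other side stands.

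- *An early decision variable need not equal the endpoint.* This is correct. Branching on a request at one month is a legitimate SMART choice, and responders need not be re-randomized.
- *A reader might infer that the request is the trial's response rule.* The documents do not say so. They name no such rule, and Phase 2 also takes people who never completed Phase 1. What can be said is that the request acts as the branching variable for Phase 1 completers.
- *A reader might infer that no treatment sequence can be estimated for requesters who do not screen.* This does not follow. They are still assessed by record review at 6, 12 and 18 months, so a sequence of first message, request, then kit and reminders includes them and can be estimated. Only the effect of a second message in them cannot.
- *They are not left without contact.* Quality control calls cover patients with no result in the record, and kit reminders go to those who were mailed a kit. These are support, not randomized stages. Phase 3 encourages repeat screening, so limiting it to people with a first screen suits its purpose.
- *Already-screened patients should be few.* This is also fair. Entry requires being out of guidelines, and other screening would have to occur in roughly the first month. Someone who obtained a kit from the outreach team may have asked for it, and so may count as a requester. But Section 5 collects the status and does not use it in the Phase 2 rule.

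**Conclusion.** The point holds as a modest, cheaply removed weakness. Applied literally, the Phase 2 rule re-invites patients whose initial screening can no longer change. This attenuates the second-stage comparison and does not bias it, provided second-stage randomization balances these patients. If 2-10% of non-requesters are affected, the attenuation among them is about 2-10%. That range is an assumption, and the true share is probably small.

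Requesters without a completed screen fall outside Phase 2 and, on the Section 6 wording, outside Phase 3. They remain analysable for the primary outcome, but second-stage message effects do not extend to them. Their number cannot be derived from the documents.

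A reader might go further and conclude that a completed test should replace the request at one month. The plan's timetable does not support this: many requesters would still be within their kit-return period and would be classed as non-responders too early.

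**What to change.** 1. In Section 5, before each Phase 2 contact and before any second-stage assignment, check the post-intervention screener (where completed) and Epic. Leave out of Phase 2 anyone with a completed test or confirmed up-to-date status, and keep them in the first-stage analysis as randomized. State how a positive stool test awaiting colonoscopy is classed, since Section 5 does not count it as compliant on its own.
2. Name the request explicitly as the one-month decision variable, if it is to stay, and give the reason for choosing it.
3. Reconcile the requesting, responding and completing wordings in Sections 5 and 6, so that Phase 2 and Phase 3 entry can each be determined from the record.
4. State that second-stage conclusions apply only to groups eligible for Phase 2, and report requesters without a result as a separate group.

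The cost is one look-up per patient in a system already monitored, a slightly smaller Phase 2 group, and a short protocol edit. Sample size and the one-month time point are unchanged.

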## **6. Study Design**

We will evaluate the VHT intervention using a fractional factorial experimental design embedded within a sequential, multiple assignment, randomized trial (SMART). The fractional-factorial design allows estimation of the optimal tailored message assuming only lower-order interactions and requires far fewer samples. For example, a full factorial design of 10 factors at two levels would involve runs of size 4,096 whereas a fractional factorial design that does not confound any pairwise interactions would involve runs of size 79. In short, the fractional factorial experimental design allows us to go beyond simply testing the efficacy of tailored vs. non-tailored messages by honing in on the specific elements of a message that are most salient to the patient.

We will also collect longitudinal data on outcomes associated with exposure to the intervention (Phase 3). Participants in the treatment arms who have completed their initial screening within the first 12 months of the study will receive an email invitation one year after the intervention. This message will invite them to view a booster of the intervention consisting of another message encouraging repeated screening. Compliance will be assessed via self-reporting and MRR for all patients as well as through tracking in MyUFHealth.

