We will also recruit patients through Facebook (See Social Media Advertising Campaign). Ads will be posted through the official UF Studies Facebook page ([www.facebook.com/ufstudies](http://www.facebook.com/ufstudies)) with assistance from the CTSI Recruitment Center, and UFHCC COE. The ads will link to the study Qualtrics portal previously described.

Approximately one week after initial contact, the patients that have not enrolled will receive an email message reminding them about the study (English and Spanish - Phase 1 Enrollment Reminder Script: E-mail). Patients who are enrolled in MyChart, either through the study or otherwise, will receive additional weekly reminders about completing the study (English and Spanish - Phase 1 Enrollment Reminder Script: Phone/Voicemail and Phase 1 Enrollment Reminder Script: Text message).

In light of COVID-19, staff were added to conduct quality control calls and add video conferencing to replace face-to-face assistance to participants. Staff in addition to community health workers (CHWs) on the research team will contact participants for quality control. Communication activities have transitioned to Zoom-PHI video conference calls for assistance with technical issues enrolling in the intervention.

Intervention: Patients will interact with an online educational application which delivers an educational message about FIT screening (Phase 1). They will be randomly assigned to receive a standard, text-based tailored message or a tailored message delivered by a virtual human. The message itself is

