comprised of a brief core message about the importance of screening as well as up to 10 additional constructs which may influence decision to screen: message source, perceived severity, risk probability, perceived susceptibility, framing, perceived benefits, response efficacy, perceived barriers, narrative persuasion, and self-efficacy. In both conditions, the information is presented to patients as coming from a “virtual healthcare assistant” in the form of either VHT or a still image. Participants will be randomly assigned to see either a demographically-concordant or demographically-discordant virtual healthcare assistant. Patients seeing a concordant assistant will be matched based on race and gender. Participants seeing a discordant assistant will be mismatched on race or gender or both. Participants whose preferred language as listed in Epic is Spanish, or who were recruited through Qualtrics and self-selected Spanish as their preferred language, will receive a Spanish-language version of the intervention.

In both the text-based and virtual human versions of the intervention, some patients will randomly see constructs featuring interactions with the virtual human. These interactive segments ask patients information about their behaviors related to CRC and screening, such as the frequency with which they eat red meat and potential barriers to screening they face. These questions will be used to randomly deliver either a tailored response to the patient’s feedback or a generic, non-tailored response.

Upon completion of the interaction with the app, patients will complete a short (i.e., 20 minute) algorithmic questionnaire that utilizes survey responses to assess attitudes and screening behaviors associated with CRC. Participants recruited through the IDR and UF Qualtrics will complete the questionnaire using web-enabled devices such as computers or tablets. Participants in phase 1 will be remunerated \$30.00 for interacting with the app and completing the subsequent questionnaire.

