### **Sample Size Analysis**

At each stage of randomization, the combination of tailored messaging factors follows a resolution 5 fractional factorial design. A sample size of 1,000 patients is sufficient to detect inferiority at a margin of 0.075 with 80% power. We note that performing this sample size calculation is non-standard as it requires estimating the best tailoring message, which requires optimizing over a potentially large number of potential tailored message combinations; we corrected for these multiple comparisons by inverting a projection interval. However, we plan to follow patients for a total of two years. Assuming 33% attrition over this time period, an initial sample of 1,500 is sufficient.

Primary endpoints include compliance with screening recommendations (measured via MMR) as well as potential mediators of intervention effectiveness (such as exposure to the intervention, psychological processing of content, and self-reported communication with a healthcare provider about screening).

Secondary endpoints including cancer detection rates as well as long-term behavioral changes (i.e. whether patients request screening the following year). They will be analyzed as descriptive statistics without anticipated power calculations.

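### Does the mismatched factor count in the Study Design example (10 two-level factors, 4,096 and 79 runs) call for a change to the plan?

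*Combined protocol and SAP*

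**What the plan says.** Section 6 (Study Design) describes a fractional factorial embedded in a SMART. It says the fraction permits estimation of the best message "assuming only lower-order interactions and requires far fewer samples". As an example it states that "a full factorial design of 10 factors at two levels would involve runs of size 4,096". The second half of the same sentence turns to the alternative and gives its size: "a fractional factorial design that does not confound any pairwise interactions would involve runs of size 79".

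The Sample Size Analysis says that at each randomisation "the combination of tailored messaging factors follows a resolution 5 fractional factorial design". It adds that the calculation is non-standard because it involves "optimizing over a potentially large number of potential tailored message combinations", and that a projection interval was used to correct for this. It gives 1,000 patients, a margin of 0.075, 80% power, 33% attrition and an initial sample of 1,500.

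Section 5 (Patient Eligibility and Recruitment) says the message contains up to ten constructs: "message source, perceived severity, risk probability, perceived susceptibility, framing, perceived benefits, response efficacy, perceived barriers, narrative persuasion, and self-efficacy". The same section has two further randomised contrasts. One is delivery mode: "They will be randomly assigned to receive a standard, text-based tailored message or a tailored message delivered by a virtual human". The other is concordance: "Participants will be randomly assigned to see either a demographically-concordant or demographically-discordant virtual healthcare assistant".

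**The concern.** A reader who checks the example finds that 2^10 is not 4,096. The second figure, 79, looks wrong too, because ten factors need only 56 coefficients for an intercept, main effects and pairwise interactions. Both printed figures point to 12 factors, so the text seems to have been written with one factor count and calculated with another.

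Three things could be at stake. First, the example supports the claim that the fraction saves many runs, and the wrong numbers could exaggerate that saving. Second, no other sentence in the plan gives a number of combinations or runs, so the slip leaves it unclear whether the factorial has 10 factors or 12. Third, the correction for searching over message combinations depends on how many there are. If the sample-size work had used the wrong count, the 1,000 could be affected.

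**Working it through.** **Inputs.** Section 6: 10 factors, two levels, 4,096 runs for the full factorial, 79 for the fraction. Sample Size Analysis: resolution 5, 1,000 patients, 33% attrition, 1,500 enrolled.

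**Step 1: try to reproduce the printed figures.** The full factorial for k two-level factors has 2^k combinations. The intercept, main effects and pairwise interactions number 1 + k + k(k − 1)/2.

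| k | 2^k | 1 + k + k(k − 1)/2 |
|---|---|---|
| 10 | 1,024 | 1 + 10 + 45 = 56 |
| 11 | 2,048 | 1 + 11 + 55 = 67 |
| 12 | 4,096 | 1 + 12 + 66 = 79 |
| 13 | 8,192 | 1 + 13 + 78 = 92 |

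With k = 10 neither figure is reproduced; 4,096 is four times 1,024. With k = 12 both are. A different count, 1 + 13 × 12/2 = 79, also gives 79, but it leaves out the main effects and would go with 8,192. The joint match is therefore to 12.

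**Step 2: is 79 itself wrong for ten factors?** Not necessarily. The base run, 10 single flips and 45 double flips make 56 runs, which are just enough to estimate all 56 terms. Adding 23 further distinct combinations gives 79 runs in which all 56 terms remain estimable, with 79 − 56 = 23 residual degrees of freedom. If not confounding means only that every pairwise term can be estimated, 79 runs are more than ten factors need, but the statement is not false. For 12 factors, 79 is the bare minimum and leaves no residual degrees of freedom from the distinct combinations.

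**Step 3: does 79 describe the resolution 5 design?** A search over regular two-level fractions found that 64 runs are too few for 10 factors and 128 suffice, and that 128 are too few for 12 and 256 suffice. So 79 is not the size of a regular resolution 5 fraction for either count. The plan does not say that the fraction is regular.

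**Step 4: does the illustrated claim survive?** Run savings under the possible readings:

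- As printed, or 12 factors throughout: 4,096/79 = 51.8-fold.
- 10 factors at the minimum of 56 runs: 1,024/56 = 18.3-fold.
- 10 factors with 79 runs kept: 1,024/79 = 13.0-fold.
- Regular resolution 5 fractions: 1,024/128 = 8-fold for 10 factors, 4,096/256 = 16-fold for 12.

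The size of any overstatement depends on the convention chosen, but the fraction is far smaller than the full factorial in every case.

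**Step 5: does the error reach the sample size?** The 1,500 comes from 1,000 and attrition: 1,000/0.67 = 1,493, and 1,500 × 0.67 = 1,005. No factor count enters. The 1,000 is attributed to a margin, a power and a projection-interval correction. The Sample Size Analysis uses neither 4,096 nor 79, and does not refer to the example. A fraction of either size also fits within 1,000 patients: 1,000/128 = 7.8 patients per run for 10 factors, and 1,000/256 = 3.9 for 12.

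**The case for a change.** The strongest case for a change is that the slip hides the factor count. Ten constructs plus delivery mode plus concordance make 12, which is exactly what the two figures imply, so 10 may be the wrong number. The multiplicity correction depends on this count, and a corrected sentence with a short factor list would cost almost nothing.

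Part of this stands. The sentence is inconsistent, and the documents do not show which number was meant or which count the sample-size work used. The 10 + 2 reading, however, is selective. Message source is already among the ten constructs and may overlap with the two added contrasts. Section 5 also randomises tailored against generic responses, and section 7 (Data Management) describes a video or a written recruiting message. Counting these would give totals other than 12. The more direct reading is that the tailored messaging factors in the Sample Size Analysis are the ten constructs named in section 5, in line with the 10 in the example.

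The worry about the multiplicity correction is only a possibility. Correcting the example would not reveal what the projection-interval calculation used, and nothing in the documents suggests that it took its count from this sentence. Listing the factors and stating the run size would add useful detail, but would not remedy any shown error in the design or analysis.

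**Conclusion.** The example contains a clerical slip: 4,096 does not belong to ten two-level factors, and 4,096 and 79 together belong to 12. The discrepancy is a factor of 4 in the full-factorial figure. The 79 is not shown to be impossible as a run size for ten factors, although it is not the size of a regular resolution 5 fraction for 10 or for 12.

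No change to the plan follows. The numbers only illustrate a general point, and that point holds on every reading, with a saving of at least 8-fold. The stated sample size is not derived from them, and no effect on power, conduct or conclusions is shown. Those building the fraction must in any case work from the actual list of factors, not from this sentence.

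This rests on taking the Sample Size Analysis at face value, as a calculation separate from the example. The documents do not give enough to reproduce the 1,000, and correcting the sentence would not alter that.
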